4.1.2 Recording of Adverse Events

Throughout the course of the study, all efforts will be made to remain alert to possible adverse events or untoward findings.

All adverse events whether volunteered by the participant, discovered by study personnel during questioning, or detected through physical examination, laboratory test, or other means will be reported on a web-based case report form specifically for adverse event reporting.

The study investigator will assess the relationship of each adverse event to be related or unrelated to study drug by determining if there is a reasonable possibility that the adverse event may have been caused by the treatment. Reasonable possibility is not the same as “any possibility.” The following should be considered when evaluating the relationship:

- Timing of event
- Patient’s history

- 472 • Prevalence of finding in population at risk
- 473 • Other possible causes - diseases, exposures, therapies, etc
- 474 • Known pharmacology of study drug (and control) or side effect of drug
- 475

476 The intensity of adverse events will be rated on a three-point scale: (1) mild, (2) moderate, or (3)
477 severe. It is emphasized that the term severe is a measure of intensity: thus, a severe adverse event
478 is not necessarily serious. For example, itching for several days may be rated as severe, but may not
479 be clinically serious.

480 Adverse events that continue after the study participant's discontinuation or completion of the study
481 will be followed until their medical outcome is determined or until no further change in the
482 condition is expected.

483 Each reported adverse event is reviewed by the Medical Monitor to verify the coding and the
484 reporting that is required. Adverse events will be coded using the MedDRA dictionary.

485 486 **4.1.3 Reporting Serious or Unexpected Adverse Events**

487 A serious adverse event is any untoward occurrence that:

- 488 • Results in death
- 489 • Is life-threatening (a non-life-threatening event which, had it been more severe, might have
490 become life-threatening, is not necessarily considered a serious adverse event)
- 491 • Requires inpatient hospitalization or prolongation of existing hospitalization
- 492 • Results in significant disability/incapacity
- 493 • Is a congenital anomaly/birth defect
- 494 • Could have resulted in death, be life-threatening, or require hospitalization without medical
495 or surgical intervention to prevent any of these events

496
497 Serious or unexpected adverse events must be reported to the Coordinating Center immediately via
498 completion of the online serious adverse event form.

499
500 The Medical Monitor responsible for reviewing serious or unexpected adverse events is:

501
502 [name]., Ph.D.
503 Jaeb Center for Health Research
504 [name]
505 [name]
506 [contact]
507 [contact]
508 Email: [contact]

509
510 The Coordinating Center will notify all participating investigators of any adverse event that is
511 serious, related to the study drug or procedures, and unexpected. Notification will be made within
512 10 days after the Coordinating Center becomes aware of the event. The Coordinating Center also
513 will notify Xeris of any such events, who will be responsible for fulfilling reporting requirements to
514 the Food and Drug Administration (FDA).

515 Each principal investigator is responsible for informing his/her IRB of serious, related, and
516 unexpected adverse events and abiding by any other reporting requirements specific to his/her IRB.
517

518 **4.2 Risks**

519 **4.2.1 Potential Risks and Side Effects**

520 Glucagon has a long history of medical use in the U.S., and is currently marketed by Eli Lilly & Co.
521 as Glucagon for Injection [rDNA origin], and Novo Nordisk as GlucaGen® HypoKit®, both
522 reference listed drugs for treatment of severe hypoglycemia. Glucagon has a rapid onset of action
523 and an extremely short half-life, and its safety, efficacy and clinical pharmacology have been well
524 established.

525
526 In a Phase 2 study, Protocol No. XSGP-201, healthy, fasted adult volunteers were administered
527 rescue doses of Xeris G-Pen™ (glucagon injection) (0.5 mg and 1.0 mg) and Lilly Glucagon for
528 Injection [rDNA origin] (1.0 mg) in a randomized, crossover fashion. Overall, all Xeris and Lilly
529 treatments were well tolerated. There were no SAEs during the study, and all AEs observed were
530 transient and generally expected with rescue injections of glucagon. The most commonly reported
531 AE was injection site pain, and the incidence of this AE was significantly higher in the Xeris 0.5 mg
532 and Xeris 1 mg groups compared with the Lilly 1 mg group; however, edema and erythema at the
533 injection site occurred infrequently and did not vary significantly with treatment. Within the Lilly 1
534 mg group, the most commonly reported AE was nausea, the incidence of which was significantly
535 higher compared with the Xeris 0.5 mg and 1 mg groups. The incidences of all remaining AEs
536 were low and not notably different across treatment groups.

537
538 However, as reported by Haymond (15), when subcutaneous glucagon in dosages of 20–150 µg was
539 given to children to manage impending hypoglycemia due to gastroenteritis or poor oral intake of
540 carbohydrates, it did not result in a perceived worsening of the patient’s nausea, nor did it result in
541 emesis immediately after glucagon administration, as is commonly observed with the recommended
542 single large 500–1,000 µg rescue dose.

543
544 In Xeris’ completed Phase 2a safety/PK/PD study, Protocol No. XSMP-201, which tested 75–300
545 µg G-Pen Mini™ doses in adult T1D patients, neither nausea nor vomiting were observed with
546 doses of 75-150 µg. Nausea, but not vomiting was reported by 4/12 subjects given the 300 µg dose
547 (3 mild, 1 moderate). Since doses of subcutaneous G-Pen Mini™ (glucagon injection) given to
548 adults per this protocol will range from 75–300 µg, some nausea is possible, but the incidence is
549 expected to be relatively low and severe nausea is not expected.

550 Although available data from prior studies indicate that mini-dose glucagon is likely to successfully
551 treat mild to moderate hypoglycemia, this is not definitively proven. Therefore, there is a risk that
552 mini-dose glucagon will not work as well as glucose tablets or other oral carbohydrates and if this is
553 the case, severe hypoglycemia could result.

554 Endurance exercise, as will be performed in this study, may be associated with generalized fatigue
555 and mild to moderate hypoglycemia. In rare situations, exercise can promote myocardial infarction,
556 sudden cardiac death or arrhythmias. In persons who have proliferative retinopathy, exercise that
557 increases blood pressure significantly (>180 mmHg) can promote retinal bleeding (PMID:
558 21800941). Since all participants will be screened prior to the exercise test for diabetes-related
559 complications and glucose monitoring will be performed throughout the experiments, the risk of a
560 serious exercise-associated adverse event will be extremely remote.

561

562 The blood draws and IV placement could result in discomfort or bruising, or rarely, an infection or a
563 blood clot. Fainting may also occur. The exact blood volumes collected may vary according to
564 local IRB regulations. The maximum blood volume collected from adults >18 years will not exceed
565 250 ml at each visit.

566

567

CHAPTER 5: MISCELLANEOUS CONSIDERATIONS

568
569
570
571
572
573
574
575
576
577
578
579
580
581
582
583
584
585
586
587
588
589
590
591
592
593
594
595
596
597
598
599
600
601
602
603
604
605
606
607
608
609
610
611
612
613

5.1 Benefits

Participants may benefit by gaining a better understanding of how to prevent exercise-associated hypoglycemia.

5.2 Participant Compensation

5.2.1 Participant Reimbursement

The participant will receive \$100 for the screening visit/ VO_2 max testing and \$225 for each exercise session. Participants will receive compensation for transportation to and from each exercise session.

Participants who participate in the pilot phase will receive \$100 for the screening visit/ VO_2 max testing and \$100 for each exercise session that is part of the pilot. Participant compensation will be paid by check, merchandise gift card or money card.

Additional travel expenses may be paid in select cases for participants with higher expenses.

5.2.2 Study Costs

All study costs will be covered by the study. The participant will use his/her own pump, blood glucose meter, and CGM (if used). The participant will be asked to insert a new infusion set on the day prior to each exercise session and if CGM is used, a new CGM sensor. The participant will also be asked to perform additional blood glucose meter checks. Participants will be permitted to request reimbursement through their site for any CGM sensors, infusion sets, or blood glucose meter strips required specifically for the purpose of the study.

5.3 Participant Withdrawal

Participation in the study is voluntary, and a participant may withdraw at any time. The investigator may withdraw a participant who is not complying with the protocol. For participants who withdraw or are withdrawn, their data will be used up until the time of withdrawal.

Participants will not be withdrawn from the study if the study drug is discontinued due to adverse events.

5.4 Confidentiality

For security and confidentiality purposes, participants will be assigned an identifier that will be used instead of their name. Protected health information gathered for this study will be shared with the Coordinating Center, the Jaeb Center for Health Research in Tampa, FL. Information also may be provided to Xeris, Inc which is providing the glucagon for the study, and Unitio, Inc., which is a T1D Exchange collaborating organization.

Some of the study data will be entered on the Coordinating Center's secure website through an SSL encrypted connection. The Coordinating Center websites are maintained on Unix and Linux servers running Apache web server software and on a Windows server running IIS, all with strong encryption. The study website is password-protected and restricted to users who have been authorized by the Coordinating Center to gain access. No identifiable health information of an enrolled participant will be released by the Coordinating Center.

614 **5.5 Discontinuation of Study**

615 Participation of a participant can be discontinued at any time at discretion of the investigator,
616 particularly if the investigator believes that there is a safety concern with continued participation.

617
618 The study can be stopped by the Steering Committee if events occur that warrant discontinuation of
619 the study.

620

CHAPTER 6: STATISTICAL CONSIDERATIONS

The approach to sample size and statistical analyses are summarized below. A detailed statistical analysis plan will be written and finalized prior to the completion of the study.

6.1 Sample Size

A target of 16 subjects, with replacement of any participants who do not complete the study, was selected as a reasonable sample size for this feasibility study. Considering the primary outcome of glucose, power was approximated using a t-test. The table below provides power estimates based on a paired t-test comparing glucose during the mini-dose glucagon treatment and glucose during the control treatment.

Power Estimates*

Mean difference (mg/dL)	Correlation						
	0.2	0.3	0.4	0.5	0.6	0.7	0.8
20	32%	35%	40%	47%	55%	68%	84%
25	46%	51%	57%	65%	74%	85%	96%
30	60%	66%	73%	80%	88%	95%	99%
35	74%	79%	85%	91%	96%	99%	>99%

*Power was calculated for a sample size of 16 participants with a two-sided alpha of 0.05 and assuming a standard deviation of 40 mg/dL for each treatment. (A previous DirectNet exercise study was considered when estimating standard deviation [16].)

6.2 Analysis Plan

6.2.1 Primary Outcome

The primary outcome for this study will be glucose, as measured by YSI analysis, during exercise and early recovery.

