Patients on insulin pump therapy have the flexibility to reduce basal insulin delivery in anticipation of exercise and in recovery to help guard against hypoglycemia. The International Society for Pediatric and Adolescent Diabetes guidelines recommend that basal insulin reductions should be done 60-90 minutes before the start of exercise so that circulating insulin levels are lowered by the start of the activity (12). This is a somewhat cumbersome and unpredictable task that is usually not performed correctly, even by the most educated and motivated patients. Since glucose production by the liver during moderate intensity exercise is primarily facilitated by a rise in the glucagon to insulin ratio (13) and patients with T1D have a reduction in this ratio during exercise because of a relative peripheral hyperinsulinemia (13) and impaired glucagon secretion (14), it may be better to attempt to change this ratio by the administration of glucagon at the onset of exercise. The recent development of a more stable form of soluble glucagon (e.g. G-Pen Mini™ glucagon from Xeris Pharmaceuticals, Inc. (Xeris)) has given researchers and clinicians the possibility of using this product as a preventative strategy to combat exercise-associated hypoglycemia. However, to date, studies have not been done that examine the efficacy of mini-dose glucagon administration for exercise.

103 **1.2 Synopsis of Study Protocol**

104 This project focuses on the development of a new strategy for the prevention of exercise-
105 associated hypoglycemia using mini-dose glucagon.

106

107 **1.2.1 Objectives**

108 The primary objective of the protocol is to determine if the administration of mini-dose glucagon
109 administered subcutaneously just before exercise produces better glucose stability than no
110 adjustments for moderate intensity exercise in patients with T1D. It will also be assessed
111 whether mini-dose glucagon before exercise produces better glucose stability than basal insulin
112 reductions or extra carbohydrate consumption. In addition, the impact of mini-dose glucagon
113 administration before exercise on nocturnal glycemia after exercise will be evaluated.

114

115 **1.2.2 Study Design**

116 This is a randomized, 4-way crossover trial.

117

118 **1.2.3 Major eligibility criteria**

- 119 • Clinical diagnosis of presumed autoimmune type 1 diabetes, receiving daily insulin
- 120 • Age 18-<65 years
- 121 • Duration of type 1 diabetes ≥ 2 years

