6.2.3 Secondary Outcomes

The following outcome measures will also be analyzed.

- Occurrence of hypoglycemia (<70 mg/dL) as measured by YSI analysis during exercise or early recovery

- 661 • Occurrence of hyperglycemia (≥ 270 mg/dL) as measured by YSI analysis in the following
- 662 time periods: during exercise, after exercise in early recovery/prior to meal ingestion and for
- 663 90 minutes after the meal (2 hours after the end of exercise)
- 664 • Glucose levels during exercise and early recovery (venous plasma)
- 665 • Glucose levels after a standardized meal (glucose area under the curve analysis, venous
- 666 plasma)
- 667 • Glucose levels in late recovery (afternoon and overnight following the exercise protocols-
- 668 CGM analysis)
 - 669 ○ Mean
 - 670 ○ Nadir
 - 671 ○ Area above and below curve threshold (i.e. area above or below 70-180 mg/dL)
 - 672 ○ % of time in range (70-180 mg/dL)
 - 673 ○ % of time below 70 mg/dL
 - 674 ○ Occurrence of hypoglycemia (< 70 mg/dL) overnight
- 675 • Carbohydrate intake (before, during and for 30 min post exercise)
- 676 • HR and ratings of perceived exertion
- 677 • Insulin and glucose counterregulatory hormones (glucagon, GH, catecholamines, cortisol)
- 678 • Inflammatory cytokines (TNF α , IL-6)
- 679 • Metabolites (nonesterified fatty acids, β -hydroxybuterate, lactate)

680
681

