T1D Exchange[®]

1

2

THE USE OF MINI-DOSE GLUCAGON TO PREVENT EXERCISE-INDUCED HYPOGLYCEMIA IN TYPE 1 DIABETES

Statistical Analysis Plan v. 1.0
Protocol v. 3.0

February 24, 2017

3

Version History

Version Number	Author	Approver	Effective Date	Study Stage	Revision Description
1.0	[name]	[name]	February 24, 2017	Data collection in progress; no analyses performed	Original version

4

5

6 **1.0 Study Overview**

7 This project focuses on the development of a new strategy for the prevention of exercise-
8 associated hypoglycemia using mini-dose glucagon.

9
10 The primary objective of the protocol is to determine if the administration of mini-dose glucagon
11 administered subcutaneously just before exercise produces better glucose stability than no
12 adjustments for moderate intensity exercise in patients with T1D. It will also be assessed
13 whether mini-dose glucagon before exercise produces better glucose stability than basal insulin
14 reductions or extra carbohydrate consumption.

15
16 Subjects 18 to <65 years old with type 1 diabetes (T1D) for at least 2 years and receiving daily
17 insulin who exercise regularly will be enrolled into the multi-center study. The study is a
18 randomized, 4-way crossover trial.

19
20 Each participant will undergo four aerobic exercise sessions (in random order) in the
21 CRC, with different strategies for glucose regulation:

- 22 • Control Trial: Fasted exercise, no basal insulin reduction
- 23 • Strategy 1: Fasted exercise, basal insulin reduction only (50% reduction in basal rate
24 five minutes before exercise, for the duration of the exercise)
- 25 • Strategy 2: Fasted exercise, no basal adjustment + pre-exercise glucose tabs (buccal
26 route-40 grams in total)
- 27 • Strategy 3: Fasted exercise, no basal adjustment + pre-exercise mini-dose glucagon
28 (sc)

29
30 In all 4 sessions, aerobic exercise will be performed in the fasted state (before a
31 standardized meal) for 45 minutes at ~50-55% of the participant’s pre-determined aerobic
32 capacity (determined by VO2 max test at screening visit).

33
34 **2.0 Sample Size**

35 A target of 16 subjects, with replacement of any participants who do not complete the study, was
36 selected as a reasonable sample size for this feasibility study. Considering the primary outcome
37 of glucose, power was approximated using a t-test. The table below provides power estimates

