38 based on a paired t-test comparing glucose during the mini-dose glucagon treatment and glucose
39 during the control treatment.

40
41 **Power Estimates***

Mean difference (mg/dL)	Correlation						
	0.2	0.3	0.4	0.5	0.6	0.7	0.8
20	32%	35%	40%	47%	55%	68%	84%
25	46%	51%	57%	65%	74%	85%	96%
30	60%	66%	73%	80%	88%	95%	99%
35	74%	79%	85%	91%	96%	99%	>99%

42 *Power was calculated for a sample size of 16 participants with a two-sided alpha of 0.05 and assuming a standard
43 deviation of 40 mg/dL for each treatment. (A previous DirectNet exercise study was considered when estimating
44 standard deviation [Tsalikian 2006].

45

46 **3.0 Analysis Plan**

47

48 **3.1 Sample collection**

49 Blood samples collected through a venous catheter with plasma glucose measured by an YSI
50 analyzer. Blood samples will be collected at:

- 51 • Baseline (at -30, -15, -5, 0 min)
- 52 • During exercise (at 5, 10, 15, 25, 35, 45 min)
- 53 • In recovery post exercise (at 50, 55, 60, 75 min)
- 54 • Regularly following a standardized mixed meal for 90 minutes (at 90, 105, 120, 135, and
55 165 min)

56

57 **3.2 Definitions of Time Periods**

- 58 • Exercise—45 minutes of scheduled exercise, even if participant terminated exercise early
- 59 • Early recovery—all time points through 30 minutes post exercise session
- 60 • Late recovery—all CGM data through noon the day after each exercise session will be
61 included. Periods of interest during late recovery include the below. Timing of meals
62 indicated on participant log; if log is missing or incomplete, meal timing will be
63 estimated.
 - 64 ○ Standard meal during study (30 minutes post exercise) to standard box lunch
65 provided at discharge
 - 66 ○ Box lunch provided at discharge to dinner (of participant's choice)
 - 67 ○ Dinner to 10:00 PM
 - 68 ○ 10:00 PM to 8:00 AM the day following exercise
 - 69 ○ 8:00 AM to noon the day following exercise

70

71 **3.3 Primary Outcome**

72 The primary outcome for this study will be glucose, as measured by YSI analysis, during
73 exercise and early recovery.

74

75 **3.3.1 Primary Analysis**

76 The primary analysis for this study will be a descriptive comparison of glycemic response during
77 exercise and early recovery between the mini-dose glucagon group (strategy 3) and the control
78 group. Summary statistics will be calculated. In the event that exercise is terminated early due to

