79 glucose <70 mg/dL and the participant is treated for hypoglycemia (or if participant is treated for
80 hypoglycemia during early recovery [prior to the meal]), the nadir glucose value will be carried
81 forward through the end of early recovery.

82

83 Analysis will follow the intent-to-treat principle with each visit allocated to one of the above
84 strategies (Section 1.0) according to the randomization assignment. Analysis will include
85 subjects who completed both the mini-dose glucagon and the control exercise session visits with
86 baseline glucose and at least three YSI glucose measurements during exercise and at least two
87 YSI glucose measurements during early recovery available from each visit.

88

89 To obtain a test of significance, a treatment comparison of glucose during exercise and early
90 recovery will be completed using a linear mixed model with repeated measures that accounts for
91 the correlation due to the cross-over design and the correlation due to multiple measures,
92 adjusting for baseline glucose level and any period effect. Regression diagnostics will be
93 performed and if the distribution of residuals is skewed, non-parametric methods and
94 transformations will be considered.

95

96 **3.4 Secondary Outcomes**

97 The following outcome measures will also be analyzed.

- 98 • Occurrence of hypoglycemia (<70 mg/dL) as measured by YSI analysis during exercise
99 or early recovery, at the visit level
- 100 • Occurrence of hyperglycemia (≥ 250 mg/dL) as measured by YSI analysis in the
101 following time periods: during exercise, after exercise in early recovery/prior to meal
102 ingestion and for 90 minutes after the meal (2 total hours after the end of exercise), at the
103 visit level
- 104 • Glucose levels after a standardized meal (glucose area under the curve analysis)
- 105 • Glucose levels in late recovery (afternoon and overnight following the exercise protocols-
106 CGM analysis)
 - 107 ○ Mean
 - 108 ○ Nadir
 - 109 ○ Area above and below curve threshold (i.e. area above or below 70-180 mg/dL)
 - 110 ○ % of time in range (70-180 mg/dL)
 - 111 ○ % of time below 70 mg/dL
 - 112 ○ Occurrence of hypoglycemia (<70 mg/dL) overnight

113

114 For sensor data after an exercise session to be included in the analysis, a subject must have at
115 least 12 hours (i.e., 144 CGM readings) from the window after the exercise session through noon
116 the following day.

117

118 **3.4.1 Secondary Analyses**

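### The SAP compares continuous glucose in exercise and early recovery with control only, although the stated aim also covers basal reduction and carbohydrate

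*Protocol*

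**What the plan says.** Protocol 1.2.1 states the primary objective as whether glucagon "administered subcutaneously just before exercise produces better glucose stability than no" adjustments. SAP 1.0 repeats it and adds the question "whether mini-dose glucagon before exercise produces better glucose stability than basal insulin" reductions or extra carbohydrate. Neither document defines stability.

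The primary outcome in both documents is YSI glucose over exercise and early recovery (Protocol 6.2.1: "The primary outcome for this study will be glucose, as measured by YSI analysis, during exercise and early recovery"; SAP 3.3 agrees). SAP 3.2 ends early recovery 30 minutes after exercise, at 75 minutes. The primary analysis (SAP 3.3.1) is a descriptive comparison of strategy 3 with control, with a mixed-model test adjusted for baseline and period. Its analysis set is "subjects who completed both the mini-dose glucagon and the control exercise session visits with" enough samples at each.

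Protocol 6.2.3 also lists as secondary "Glucose levels during exercise and early recovery (venous plasma"). SAP 3.4 has no such line. SAP 3.4.1 compares strategy 3 with each other strategy, but its text concerns the secondary outcomes. The in-window outcomes left in SAP 3.4 are two yes/no items: glucose below 70 mg/dL and glucose of 250 mg/dL or more.

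**The concern.** One of the two stated questions, glucagon against basal reduction and against tablets, loses its continuous in-window outcome between Protocol and SAP. An analyst who follows the SAP literally would collect the full glucose profiles for strategies 1 and 2 but compare them with glucagon only as thresholds crossed or not. Post-meal area under the curve and late-recovery CGM measures are compared across strategies, but they fall after this window.

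There is a second, smaller point. The planned test is of a signed difference in glucose level, while the objective speaks of stability. A higher level under glucagon may mean a fall was prevented or that glucose overshot. If the level difference is reported as better stability, the claim goes beyond the test.

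**Working it through.** **1. What the window contains.** SAP 3.1 schedules 6 exercise samples (5 to 45 min) and 4 in recovery ("In recovery post exercise (at 50, 55, 60, 75 min"), so 10 per session. Planned values: 10 × 4 sessions × 16 participants = 640, of which strategies 1 and 2 contribute 10 × 2 × 16 = 320. Those 320 enter the SAP's contrasts with glucagon only through the two thresholds.

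**2. The plan's own power figure.** Inputs (Protocol 6.1, SAP 2.0): n = 16, SD 40, two-sided alpha 0.05, paired t-test. SD of the difference = 40 × √(2(1 − ρ)), which is 40 at ρ = 0.5. Noncentrality = 30 / (40/√16) = 3.0 on 15 df, critical t = 2.131. Power = 80.1%; the table gives 80%. At ρ = 0.2 and 0.8 the results are 60.2% and 99.3% (table: 60% and 99%). The table covers glucagon against control. Applying its inputs to strategies 1 and 2 is an assumption, since the documents give none for those pairs.

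**3. The same shift cut at 70 mg/dL.** Assumptions not in the documents: the session nadir is bivariate normal with ρ = 0.5 and a shift of 30, and an exact McNemar test stands in for the logistic mixed model. Example with SD 40 and lower-arm mean nadir 70:
- P(<70) is Φ(0) = 50% in the lower arm and Φ(−30/40) = 23% in the other.
- Discordant pairs occur with probability 32.6% in one direction and 5.2% in the other.
- With 16 pairs, significance needs a split such as 6–0 (p = 0.031) or 8–1 (p = 0.039); 5–0 gives 0.063.
- Power is 24.6%.

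Repeating this over lower-arm mean nadirs from 40 to 140 in steps of 5, for several nadir SDs:

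| Nadir SD | Maximum power | Mean nadir 70 | Mean nadir 90 |
|---|---|---|---|
| 40 | 28% | 25% | 11% |
| 30 | 53% | 43% | 10% |
| 25 | 72% | 57% | 7% |
| 20 | 91% | 73% | 3% |

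The maximum falls at a lower-arm mean nadir of 55. At SD 40, varying ρ from 0.2 to 0.8 moves it only from 25% to 31%. The loss therefore depends strongly on the assumed nadir SD and mean. A smaller SD would also raise continuous power if it applied to level, so the rows below SD 40 should not be set directly against 80%.

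**4. The upper threshold.** Sessions start at 100–140 mg/dL (Protocol 3.2.1), so reaching 250 takes a rise of 250 − 140 = 110 to 250 − 100 = 150 mg/dL. A moderate overshoot is not recorded.

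**5. Level against stability.** Let control depart from baseline by c on average and glucagon by c + D. Then |c + D| < |c| only if control falls by more than D/2, which is 10 to 17.5 mg/dL for the plan's D of 20 to 35. For a normal departure with mean μ and SD 40, the mean absolute departure is 40√(2/π)·exp(−μ²/3200) + μ(1 − 2Φ(−μ/40)). With D = 30, three control/glucagon pairs all give about 80% power on level:
- −30/0: mean absolute departure 40 against 32, glucagon better.
- −15/+15: 34 against 34, equal.
- 0/+30: 32 against 40, glucagon worse.

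**The case against.** The strongest reply is that the comparison is already planned. Protocol 6.2.3 lists the outcome, Protocol 6.2.4 covers primary and secondary outcomes, and the SAP nowhere says the item is withdrawn. The line may have been left out simply because it repeats the primary outcome. That is quite possible, and a reader should not infer a deliberate withdrawal. It does not close the gap, however. The general contrast in Protocol 6.2.4 is each strategy against control. It names strategy 3 against the others only for binary outcomes and gives no contrast for continuous ones.

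A second reply is that this is a feasibility study with a descriptive primary analysis, and that against control a higher level is a fair sign of a prevented fall, since Protocol 1.1 expects glucose to drop when basal insulin is unadjusted. That stands. A reader might infer that the stability objective has no result at all, but the documents do not support this. Summaries of the glycemic response by arm would show an average overshoot, and the two threshold outcomes capture departures in both directions.

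A reader might also infer that no direction is expected against either active comparator. That holds for tablets but not clearly for basal reduction. The rationale in Protocol 1.1 describes guideline reductions made 60–90 minutes ahead and argues that glucagon at exercise onset may be better, while strategy 1 as studied starts five minutes before exercise.

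Finally, it is tempting to read 28% as a ceiling on power for the hypoglycemia outcome. It is not one, because it depends on giving the nadir an SD that the plan states only for glucose by treatment.

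**Conclusion.** The concern holds as a mismatch between Protocol and SAP that should be corrected. Followed literally, the SAP makes no continuous comparison of in-window glucose between glucagon and strategies 1 or 2, although that is a stated question. This rests on the text alone and is secure.

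The size of the loss is less certain. The continuous outcome has 80% power for 30 mg/dL under the plan's inputs, assuming they carry over to these pairs. The below-70 outcome has at most about 28% at nadir SD 40 and 72% at SD 25, and about 11% or less at either SD when the lower arm's mean nadir is 90 or more.

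The primary analysis itself stands. The wording limit also holds, because one level difference is compatible with better, equal or worse stability. It does not follow that a new stability index must be tested. For the −30/0 case above, a paired test of absolute departure has only about 14% power at departure SD 40, and about 35% at an assumed SD of 28.5.

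**What to change.** 1. Restore YSI glucose during exercise and early recovery in SAP 3.4, with strategy 3 compared with control, strategy 1 and strategy 2 in the four-strategy model of SAP 3.4.1. Apply the carried-forward nadir and the minimum-sample rules of SAP 3.3.1 to every session. State that SAP 3.3.1 remains the primary result for glucagon against control, since the two models may give slightly different estimates.
2. Report these results as differences in glucose level and do not describe a higher level as better stability. Alternatively, reword the objective to glucose level or prevention of the fall.
3. Optional: a descriptive stability summary for each strategy, for example time-weighted absolute deviation from a named pre-dose baseline sample over 0–75 minutes, with the parts above and below baseline shown separately. Give it as an estimate with a 95% confidence interval and no test.

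The cost is one or two outcome lines and no new samples. The SAP's version history says data collection is in progress with no analyses performed, so this can still be prespecified. The downsides are one or two more outcomes without multiplicity correction, and reliance on the carried-forward nadir, which holds a treated session at its lowest value to 75 minutes. The optional measure is also likely to be right-skewed.
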